The WLM investigators recognize the appropriateness and importance of securing the cooperation of personal clinicians. To this end, the personal clinicians of all participants are sent a letter describing the trial. These letters explain the study procedures and measures, and the circumstances that would lead to referral of a participant to her/his personal clinician. At screening, persons with non-medicated diabetes, individuals with a history of a CVD event more than 12 months prior, and individuals with possible angina based on the Rose questionnaire require explicit approval of the personal clinician and a non-positive stress test or other diagnostic test for CAD within the past 12 months in order to be eligible to participate. The

angina referral is made again at baseline if applicable. However, as noted above, a stress test may be waived for participants with non-medicated diabetes or prior CVD event who are already engaging in regular vigorous activity, have obtained MD permission to participate, have a glycosolated hemoglobin less than 8.0 (for diabetics only), and meet all other eligibility requirements. Screenees without a personal care provider are assisted in finding one.

All WLM participants will be on medication for hypertension and/or dyslipidemia. Weight loss and increased physical activity may necessitate reducing medications; other situations (e.g., new onset of one of these conditions; weight re-gain) may necessitate initiating or increasing medications. The decision to initiate or adjust drug therapy is a decision of the personal clinician, not a WLM clinician. However, formal criteria based on BP measurements or symptoms trigger referral for clinician evaluation. Clinical center staff track these referrals and this information is reported to the Data and Safety Monitoring Board.

Providers of participants who, after randomization, experience a CVD event are asked to make recommendations about what level of physical activity is safe to resume. These participants are still encouraged to attend regular follow-up clinical measurement visits. Participants who become pregnant following randomization are excluded from further participation in the study and their outcome data are censored as of their estimated date of conception.

Study Oversight

A Data and Safety Monitoring Board (DSMB) provides participant safety oversight for the trial. DSMB members, who include research scientists not otherwise connected with the study, are appointed by NHLBI. The expertise of members includes the disciplines and skills needed to initially review the protocol and then to monitor trial progress, quality of data, and safety of the participants by reviewing study reports. The DSMB serves in an advisory capacity to the NHLBI. Its members have access to unblinded outcome data during the trial, and can recommend early termination of one or more arms of the trial if the data suggest significant adverse risk to participants, if the questions posed by the trial appear to have been answered and there are no ethical or other reasons to continue the trial, or if continuation of the trial is futile.

Participant Closeout

The structure and content of close-out activities is left largely up to the individual sites, but in all cases includes personalized feedback, a summary of clinical measurements (e.g., weight, blood pressure), and counseling on heart disease prevention by qualified personnel (e.g., dietitian, nurse, health educator). Close-out activities can take place in the context of either an individual exit interview or a group counseling session. Clinical centers can make alternative arrangements to provide this information to participants who are not able or willing to attend the exit interview.

At the conclusion of the full trial, study participants are informed about the overall findings of the trial. This may occur in the context of an individual interview, group meeting, or mailing.

12. Statistical Analysis Plan

Analysis of Phase I Weight Loss Data

Complete results from the Phase I weight loss program will be available by the end of the second year of the study. Since these run-in data will be collected before randomization, they will be available for analyses and publication before the end of the trial. These secondary analyses will focus on the relationships between participant characteristics, adherence to the treatment program, and weight loss before randomization.

Analysis of Phase II Weight Loss Data

Primary Analysis sample

The planned primary analysis sample is intent-to-treat (ITT). In this approach, all persons who were randomized are included in the analysis in the assigned treatment group, regardless of actual treatment. If randomized individuals were not measured on the primary outcome post-randomization, we will impute an outcome for the ITT based on pre-randomization data and likelihood-based estimates (see missing data imputation, below).

We will exclude cases randomized in error or admitted to Phase I in error from the ITT analysis, except for those exceptions approved specifically by the Steering Committee for inclusion in the ITT analysis. Such exclusions can be carried out without biasing the outcomes analysis if they occur no more than 6 months after randomization, are objectively determined, carried out blinded to information about treatment assignment or outcome, and applied consistently to all affected participants. If a randomized participant is discovered to fail an inclusion/exclusion test that the Steering Committee has already waived for another participant, that second participant will also stay in the analysis sample.^{133,153}

Multi-person households

This study is somewhat unusual in that a small subset of participants is same-household pairs (usually a married couple), in which one partner is randomized and the other is assigned to the same arm. So one partner is assigned non-randomly, and, since these pairs live together, outcomes are likely to be correlated. Through August, 2004, 16 couples were randomized, or less than 2.5% of the number randomized into Phase II. Partners were accepted for entry into the study in an effort to improve recruiting success for difficult-to-recruit subgroups, particularly African-American men.

We used a stratified randomization plan with the aim of balancing the distribution of selected features across the arms of the trial. Because the randomized person is assigned to arm in a way that balances the study and the non-randomized paired person is assigned to the same arm, the inclusion of the non-randomized person potentially creates an imbalance between the two arms. In addition, we anticipate that there may be numerical problems in attempting to model the covariance within household pairs because of the very small sample involved.

In view of these considerations, the Steering Committee decided not to include the non-randomized person in the primary ITT analysis. A secondary analysis will look at the impact of including these individuals.

Outcome measures

The **primary outcome** variable is weight in kilograms, which is measured six times--at baseline/randomization (W_R), end of follow-up after 30 months (W_F), and at 6-month intervals in between (6, 12, 18, 24 months).

The feature of weight that is of primary interest is the change over 30 months, ΔW_{R-F} . If the 30-month measure is missing, we will impute the missing value (see below). In descriptive tables in our outcome papers, we will also report the weight loss data as percent loss from baseline, defined as $100 * \Delta W_{R-F} / W_R$.

The first of the two baseline weights must be measured on or after G19 or the start of week 22, whichever is earlier. The second baseline weight is taken at least one week (7 days) following the first baseline weight, and no later than on the date of the randomization visit.

Both the first baseline weight and the second baseline weight must be at least 4 kg less than the second entry weight in order for the participant to be eligible for Phase II. **The second of the two baseline weights defines the baseline weight (W_R) for analysis of post randomization weight loss maintenance.**

Secondary outcomes, *other than costs*, include measures of behavior change, psychosocial variables, and prevalence of CVD risk factors. Many of these measures may also serve as covariates (mediators or moderators of weight change) in secondary covariate analysis. As for the primary outcome, the feature of interest is change from baseline to final measure, and the same modeling methods will be used to analyze these, but without replacing missing values through imputation. The measures are defined below.

1. Behavior change:

- *Total energy intake (kcal.)*, as measured by the Block FFQ;
- *Dietary intake* of various nutrients (e.g., fats) and food groups (e.g., fruits and vegetables) (from Block FFQ);
- *Physical activity*, as measured by accelerometry and self-reports of minutes of exercise.

2. Psychosocial variables:

- *Medical Outcomes Study Short Form Health Survey (SF-36)*, 9 subscale scores (physical function, role function-physical, role function-emotional, bodily pain, general health, social function and psychological well-being /mental health, vitality health transition, and side effects checklist), plus overall scores for mental and physical well being;
- *Social Support and Eating Habits Survey* (2 subscores each for family, friends, total 4 scores);
- *Social Support and Exercise Survey* (2 subscores for family, 1 for friends, total 3 scores);
- *Perceived Stress Scale (PSS)* (4-item subset of the 14-item scale, 1 score);
- *Patient Health Questionnaire (PHQ-8)*, 1 score).

3. Prevalence of CVD risk factors:

The sample will be stratified based on baseline information into positive for the condition (i.e., medication treated or elevated) vs. neither.

- *Hypertension*: Individuals with prevalent hypertension (elevated BP or taking an antihypertensive medication at baseline) will be scored for improvement (0, neither of these is true at time F) vs. persistent hypertension (1). Individuals without hypertension at baseline will be scored as incident hypertension (1, defined by either elevated BP or taking an antihypertensive medication at time F) or persistent non-hypertension (0).
- *Hyperlipidemia*: Individuals with prevalent hyperlipidemia (fasting LDL-C \geq 130 mg/dl or taking lipid-lowering medication at baseline) will be scored for improvement (0, neither of these is true at time F) vs. persistent hyperlipidemia (1). Individuals without hyperlipidemia at baseline will be scored as incident hyperlipidemia (1, fasting LDL-C \geq 130 mg/dl or taking lipid-lowering medication) or persistent non-hyperlipidemia (0).
- *Diabetes*: Individuals with prevalent diabetes (fasting glucose \geq 125 mg/dl at baseline or self-diagnosis of diabetes) will be scored for improvement (0, fasting glucose $<$ 125 mg/dl) vs. persistent diabetes (1). Individuals without diabetes at baseline will be scored as incident diabetes (1, fasting glucose \geq 125 mg/dl or taking diabetes medication) or persistent non-diabetes (0).

Design Variables

1. Treatment:

There are three treatment groups, parameterized so that SD/UC is the reference group.

2. Sites:

There are four sites. Portland will be coded as the reference group.

Primary Covariates

The following are *primary* covariates, which will be included in the initial models testing the effect of treatment on the above primary and secondary outcomes.

1. Demographic features

- *Age in years at randomization (R)*: continuous measure;
- *Gender*: Self-reported, female (code 1) vs. male (code 0);
- *Race*: Self-reported, African-American (code 1) vs. other (code 0);
- *Race x Gender* interaction.

Missing data

The analysis of the primary endpoint will be on the intent-to-treat sample, with all missing 30-month weights to be supplied by multiple imputation. We anticipate that we will have complete data on baseline measures including the primary covariates, so that the need for imputation will arise only with respect to the 30-month (final) measure. Only this measure will be imputed.

To fill in the missing 30-month weight, we will carry out multiple imputation using SAS PROC MI (which implements algorithms given by Schafer).¹⁵⁵ We will specify the variables in the MI model in advance and obtain the approval of the Steering Committee before proceeding with this process. The MI will be completed before outcomes analysis is begun.

The goals of this process¹⁵⁶ are

- a) to assure a valid and efficient outcome analysis,
- b) to assign plausible values to participants with a missing outcome given their observed values,
- c) to preserve the correlational structure among the study measures, and

- d) to incorporate into the inferential process the uncertainty inherent in replacing missing values.

In multiple imputation, the parameters (means and covariances) of the joint distribution of observed and missing variables is estimated in an iterative fashion, starting with the observed data and plausible values for the missing values. After an estimate of the parameters for all the variables is obtained, the imputed values of missing data points are updated, and the parameters are re-estimated.¹⁵⁵ The prior joint distribution is assumed to be multivariate normal but is otherwise not specified. Simulations (e.g., in NHANES data) have shown that inferences based on MI are robust to departures from this assumption “except when the fraction of missing information is high (in excess of 50%)”.¹⁵⁵

Once stable parameter estimates are achieved, each missing value is sampled from the final (“posterior”) joint distribution and then further perturbed with random error. The selection of observed variables should be as inclusive as possible, in order to assure that any likely analyses involving the 30-month weights are nested within the MI model. For instance, by including any interim outcome measures (months 6-24) in the modeling, the within-subject trend over time is accounted for in the prediction process.²⁵

The efficiency and unbiasedness of analyses based on imputed data rest on the assumption that the data are “missing-at-random”, also called “ignorable”. Without getting too technical, the “crucial assumption made by ignorable methods is not that the propensity to respond is completely unrelated to the missing data, but that this relationship can be explained by data that are observed”.¹⁵⁵ This implies that the MI model should include all of the variables that may help predict the missing value, such as weight measured at months 6-24.

Schafer notes that ignorability is a “relative concept”. To put this in perspective, it may be helpful to note that the validity and efficiency of complete-cases analysis depends on data “missing completely at random” (i.e., unrelated to any variable observed or not observed), that maximum likelihood estimation in a random-effects model also requires MAR, and that last-value-carried-forward (a widely used strategy for replacing missing values) ignores any trend in the outcome over time and reduces the standard error, thus inflating the likelihood of observing a significant result. In short, methods that do not use multiple imputation often have more stringent assumptions or less desirable effects on the analysis results.

Imputed values will be drawn several times (most likely 5, but this needs to be determined once the parameter estimates of the imputation process are known), thus creating several “complete” versions of the dataset. The planned primary outcome analysis will be repeated in exactly the same way in each of the imputed datasets. Finally, the results will be combined using Rubin’s¹⁵⁷ rules (implemented in SAS PROC MIANALYZE) to produce the adjusted estimates and statistics from which inferences will be drawn. Only the results based on multiple imputation carried out on the cleaned and locked final data will be used in publications.

Primary Analysis statistical model

The trial’s primary specific aim is to compare the effectiveness of each of two active interventions (PC and IT) versus self-directed/usual care in maintaining weight loss from randomization (R, at the end of the initial Phase I weight-loss phase of the trial) to the end of Phase II maintenance (F), 30 months post randomization. We use E to denote an entry measure (beginning of weight-loss program, or Phase I), e.g. W_E .

Formal hypotheses:

Null hypothesis: The PC [IT] intervention does not differ from SD/UC in the change in weight over the 30-months maintenance period; this is a joint hypothesis with two parts: $\beta_1 = 0$ and $\beta_2 = 0$.

Alternate hypothesis 1. The PC intervention differs from SD/UC in the amount of weight change over the 30-months maintenance period: $\beta_1 \neq 0$ (2-sided test).

Alternate hypothesis 2. The IT intervention differs from SD/UC in the amount of weight change over the 30-months maintenance period: $\beta_2 \neq 0$ (2-sided test).

The full model for the primary hypothesis test is

$$\Delta W_{R-F} = \beta_0 + \beta_1 PC + \beta_2 IT + \beta_3 \Delta W_{E-R} + \beta_4 W_E + \sum \alpha_i S_i + \sum \delta_i E_i + e_{ij} \quad (1)$$

where PC is an indicator of the personal contact intervention; IT is an indicator of the Web-based intervention; ΔW_{E-R} indicates the change in weight from Entry to Randomization, and W_E is the Entry weight. The S_i terms are indicators of the performance sites, the E_i terms are planned additional explanatory variables, and e_{ij} is a random “error” term assumed to be normally distributed with mean zero. The additional explanatory (E’s) factors are 1) age, 2) female gender, 3) African-American ethnicity, and 4), gender x ethnicity interaction.

Under this model, β_1 represents the effect, after adjusting for all of the explanatory factors, of the PC intervention vs. SD/UC, and β_2 represents the corresponding contrast for the IT vs. SD/UC groups. Tests of the null hypotheses that $\beta_1 = 0$ and $\beta_2 = 0$ are thus the test of the primary hypothesis. Because the PC vs. IT contrast is a secondary aim, a test of the null hypothesis that $\beta_2 - \beta_1 = 0$ is done only if at least one of the previous two null hypotheses is rejected.

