Overview of PC. The PC intervention offers person-to-person guidance and support to assist participants in avoiding or overcoming obstacles that would attenuate maintenance of weight loss. This approach acknowledges that weight maintenance is a difficult task and is built on the premise that success is more likely with the assistance of a health counselor, e.g., nurse, dietitian, or physical activity coach, (i.e., a “case management approach”). It uses brief individual monthly contacts, primarily via telephone, and several face-to-face sessions to deliver an intervention composed of core elements.

Core elements. The core elements of the Personal Contact (PC) intervention include methods and strategies to assist participants in adhering to health behaviors for maintaining weight loss. These methods and strategies include frequent contacts, a mechanism for self-monitoring, tailored reinforcement messages, social support, problem solving, and relapse prevention. Motivational Interviewing approaches are used by the interventions to conduct these contacts.

Contact schedule. Participants in the PC Intervention have monthly contacts with an interventionist for 30 months. The face-to-face (FTF) intervention contacts occur approximately every four months, with telephone contacts during the intervening 3-month periods. One of the three annual face-to-face contacts should be a group session with other PC participants. If needed, there may be two additional contacts (face-to-face or by phone) at the interventionist’s discretion. This frequency of contact is based on information from previous trials on what may be an appropriate contact frequency to enhance maintenance,⁴² from experience in disease management programs,¹²⁰ and suggested frequency of face-to-face contacts from the Medicare Medical Nutrition Therapy Amendment Act of 2001.¹³⁴

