Data collection schedule. Eligibility and demographic data are collected at study entry during screening visits, prior to Phase I (the initial 5-month weight-loss program that all participants receive). The number of screening visits is not predetermined. Additional baseline data are collected at the end of Phase I for those individuals who qualify for randomization to Phase II (i.e., who have lost at least 4 kg) at additional clinic visits. The number of these clinic visits is also not predetermined. Comprehensive follow-up data are collected 12 and 30 months after randomization. Additional weight and safety measurements are obtained at 6, 18, and 24 months. The data collection schedule is summarized in Table 4. Measurement methods are described below.

	Entry Measures	Baseline Measures	Follow-up Measures				
	Phase I	End of Phase I/ Start of Phase II	Phase II (time since randomization)				
	Screening	Randomization	6 mo	12 mo	18 mo	24 mo	30 mo
Inf. consent	X	X ¹					
Demographics	X						
Internet ques	X						
Medical Hx ques	X						
Height	X						
Weight	X ²	X ²	X	X ²	X	X	X ²
Rose angina ques	X	X ¹	X	X	X	X	X
Medication ques	X	X ¹		X			X
FFQ*	X	X ¹		X			X
Accelerometry	X	X ¹		X			X
Blood pressure ³		X ¹		X			X
Fasting blood ^{4,5}	X ⁴	X ¹		X			X
Adverse event Q		X	X	X	X	X	X
Psychosocial Qs	X	X ¹		X			X
Perceptions ques	X ⁶						
Beliefs ques		X ⁷					

- 1 only collected for those eligible for Phase II. Weight and adverse event questionnaire are collected for everyone.
 - 2 weight is collected on two separate days at entry, baseline, 12, and 30 months
 - 3 blood pressure is collected on two separate occasions for each measurement point
 - 4 includes serum for analysis of glucose and lipids. Aliquots of plasma, serum, and buffy coat are collected for long-term storage
 - 5 only analyzed on individuals who are subsequently randomized to Phase II
 - 6 once, preferably during screening, but may be collected later if unable to obtain
 - 7 once during screening, but can be completed up to 4 months after the participant has enrolled in Phase 1
- * FFQ = food frequency questionnaire

Measurement methods

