This chapter describes measures to ensure the safety of participants in the WLM Trial, a study population that is at risk for complications of hypertension, diabetes, and/or dyslipidemia. In general, participants are carefully screened to insure that participation in the study does not put them at undue risk. The study's eligibility criteria serve to exclude those in whom more aggressive therapy is indicated or in whom the dietary and physical activity components of the WLM interventions might pose some risk. For example, individuals with a CVD event in the past year, and those with medication-treated diabetes are excluded. Additionally, surveillance for serious adverse events and other relevant clinical events occurs by questionnaire at regularly scheduled intervals. This chapter describes safety monitoring and management of serious adverse events.

Serious Adverse Events (SAE) Surveillance

Surveillance for SAEs and other relevant clinical events that may be associated with study participation occurs at Randomization (prior to Phase II) and at every data collection visit thereafter through the 30-month visit. This is done via several methods: 1) the Rose angina questionnaire is a well-validated tool for detecting possible angina, 2) a medication questionnaire documents changes in the use of eligibility medications (i.e., for hypertension and dyslipidemia) that may result from changes in weight and/or physical activity, and 3) the medical events screening form captures information about new CVD events and other serious or life threatening events. Any positive response on these questionnaires is reviewed by a local site clinician. Specific guidelines determine what constitutes an SAE and when and if the participant should be referred to his/her provider for additional evaluation and treatment.

Confirmed serious adverse events are reviewed at the Coordinating Center and classified as gastrointestinal, cardiovascular, musculoskeletal, or "other" in nature. This information is then reported to the DSMB and NHLBI by site and treatment arm. Similar information reported by participants at other times (e.g., during Phase I group meetings) is noted and followed up as needed to assure participant safety.

Expected Events

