1. During Phase I (weight loss program with weekly group sessions), the interventionists will remind participants at regular intervals that we are recommending moderate rather than vigorous physical activity. Participants will also be reminded at these times that, should they wish to engage in vigorous physical activity, we strongly recommend an exercise stress test (EST) and clinician permission beforehand. Recognizing that we can't control whether a participant follows these recommendations or not and that they will potentially be engaging in a number of lifestyle behaviors not prescribed or sanctioned by the study, we will request documentation of EST and provider permission, but participants will remain in the study even if they do not provide it.
2. During Phase II (maintenance phase with less frequent contact), participants are asked, as part of the clinical measurement protocol every six months, whether they are engaging in vigorous physical activity and, if yes, are referred to their primary care provider as noted above. The coordinating center will notify the clinical sites whenever a participant is engaging in vigorous physical activity and approval for such activity has not previously been documented.

Participants are informed of the potential risks, such as musculoskeletal discomfort when new types of physical activities are started. Risk of injury is minimized by instruction on proper exercise technique. As a component of Phase I, participants are taught techniques for stretching,

warm-up, and cool-down. In the case of illness or injury during Phase I, interventionists advise the participants on adapting their physical activity program. For example, individuals who have been in automobile accidents may need to alter their physical activity patterns for a time period. This alteration in activity may require some assessment in order for the interventionist to be able to provide suggestions for adapting the participant's physical activity program. A study clinician is available to advise the interventionists on the need to refer for medical care if necessary. Musculoskeletal problems that occur during Phase II and are brought to an interventionist's attention are handled similarly; an unblinded clinician is available to advise the interventionist as needed.

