If there is any question about the etiology of an injury or the need for treatment, the participant is referred to their provider for evaluation. If a participant is not willing to follow recommendations for referral care, the study clinician is notified and determines if further action is required. If appropriate, a serious adverse event report is created.

Nutrient Intake

Calorie restriction can theoretically lead to inadequate nutrition. To minimize this risk, participants are encouraged to eat a variety of foods from all food groups and to maintain an adequate calorie level. Participants are instructed not to reduce caloric intake below 1200 calories per day. During the intensive weight-loss program in Phase I, an interventionist periodically reviews food records and provides feedback on the adequacy of nutrient intake. The issue of adequate nutrient intake is discussed in the group and individual sessions. If nutritional deficiency is suspected and unresponsive to advice from the interventionist, the site clinician counsels the participant.

Participants may use extreme measures to lose 4 kg at the end of Phase I in order to be eligible for Phase II. Participants are reminded regularly of the importance of safe weight loss. Those who have a sudden, marked weight reduction are interviewed to determine if extreme measures have been taken. Interventionists are trained to detect evidence of extreme measures, and are given strategies for responding. The clinical site clinician is available to interview any participant if the interventionist or other study personnel suspects that the participant is using potentially unsafe methods.

Pregnancy and Other Exclusions

If a participant becomes pregnant during the study, she is excluded immediately from further participation in all study activities. If she has not yet seen a physician, she is immediately referred for standard prenatal care. If a participant develops any other exclusionary condition (e.g., cancer) following randomization, further participation is determined by a study clinician in conjunction with the participant's personal physician.

Contact with Personal Clinicians

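### PC may appear somewhat less safe than SD/UC in the by-arm SAE report, because SAEs found through intervention contacts are neither separated nor excluded

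*Combined protocol and SAP*

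**What the plan says.** **Scheduled route, the same in every arm.** Under Serious Adverse Events (SAE) Surveillance in Section 11, surveillance "occurs at Randomization (prior to Phase II) and at every data collection visit thereafter through the 30-month visit". Section 10 (Data collection schedule) has comprehensive visits at 12 and 30 months and adds: "Additional weight and safety measurements are obtained at 6, 18, and 24 months". That makes five visits after randomization with the adverse event questionnaire. Staff who collect follow-up data are masked to arm (Section 8, Blinding; Section 10, Masking).

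**Reporting.** Confirmed SAEs are classified at the Coordinating Center, with musculoskeletal as one of four classes. Then: "This information is then reported to the DSMB and NHLBI by site and treatment arm".

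**Off-schedule information.** The next sentence reads: "Similar information reported by participants at other times (e.g., during Phase I group meetings) is noted and followed up as needed", with participant safety given as the purpose. It does not say whether such reports enter the by-arm table.

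**Interventionist route in Phase II.** The Physical Activity subsection of Section 11 covers "Musculoskeletal problems that occur during Phase II and are brought to an" interventionist's notice. They are dealt with as in Phase I, with an unblinded clinician on hand to advise. The paragraph that follows, on referral, ends: "If appropriate, a serious adverse event report is created".

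**Contact frequency.** Section 9 (PC, Contact schedule): "Participants in the PC Intervention have monthly contacts with an interventionist for 30 months". SD/UC participants meet an interventionist at randomization, after the 12-month visit, and after the 30-month visit once data collection is complete.

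**The concern.** A between-arm comparison of SAE counts is fair only if events are looked for equally in each arm. The visit forms meet that condition. The interventionist route does not, because its use depends on how often a participant talks to an interventionist, and that frequency is what the trial randomizes. PC calls also review the past month's activity and ask for barriers, including barriers to exercise (Section 9, Telephone contacts), so injuries are a natural topic.

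SAEs rest on unverified self-report (Section 11, Expected Events), so the count depends partly on how often people are asked. The DSMB sees the counts by arm and may recommend ending one or more arms for adverse risk (Section 11, Study Oversight). An excess in PC that comes only from extra opportunities to report could not be recognized as such in that table.

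**Working it through.** **Step 1: contacts and forms between randomization and 30 months.**

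- PC: Table 3 gives 9 calls and 3 visits a year. (9 + 3) × 2.5 years = 30, which reproduces the stated monthly schedule.
- SD/UC: one meeting after randomization and before the 30-month visit. The later meeting follows that visit.
- IT: orientation and annual in-person sessions, plus phone prompts if needed and a reviewed message board. Exposure to this route is harder to count, so the check below compares PC with SD/UC.
- Scheduled questionnaires after randomization: 5 in each arm.

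**Step 2: effect on the count.** The documents give no SAE rate and no capture rate, so there is no plan figure to reproduce here. Assume the true risk is equal in both arms, and let

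- q = share of SAEs captured by the visit forms, taken as the same in both arms;
- r = share of the missed SAEs that PC contacts add to the count, with the SD/UC addition taken as zero.

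Apparent PC:SD/UC ratio = [q + (1 − q)r] / q. Its ceiling, at r = 1, is 1/q.

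| q (assumed) | r = 0 | r = 0.5 | r = 1 |
|---|---|---|---|
| 1.00 | 1.00 | 1.00 | 1.00 |
| 0.95 | 1.00 | 1.03 | 1.05 |
| 0.90 | 1.00 | 1.06 | 1.11 |
| 0.80 | 1.00 | 1.13 | 1.25 |

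The q = 0.90 row is anchored loosely on the 90% follow-up rate about one and a half years after initial weight loss (Section 15, Rationale for Phase III). That is a visit rate, not an SAE capture rate.

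**Step 3: what this means in participants.** Take 800/3 ≈ 267 per arm (equal allocation assumed) and a true 30-month SAE risk of 20% (assumed). With q = 0.90:

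- SD/UC: 267 × 0.20 × 0.90 ≈ 48.
- PC, r = 0.5: 267 × 0.20 × 0.95 ≈ 51.
- PC, r = 1: 267 × 0.20 × 1.00 ≈ 53.

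The chance of a nominal excess in PC at two-sided 0.05 would be about 5% to 9%, against 2.5% in that direction with no bias. With q = 0.80 and r = 1 the counts are 43 and 53, and the chance is 22%.

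**Step 4: the same check with a form-based comparison.** If only events recorded on the common forms are compared, r = 0 and the ratio is 1.00 for any q that is equal across arms.

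**The case against.** The strongest reply is that the main stream is balanced and the second is narrow. Section 11 says that "surveillance for serious adverse events and other relevant clinical events occurs by questionnaire at regularly scheduled intervals", on one schedule for all arms and with masked collectors. Off-schedule information is described as followed up for the participant's safety, not as counted. The sentence that allows an SAE report closes a paragraph on referral and lowers no threshold. SAEs are mostly major events such as hospitalization, major cardiovascular events and cancer. Fractures and ligament tears are asked about at every visit in every arm. An event first heard on a PC call would therefore usually be recorded at the next visit anyway. Section 12 plans no between-arm SAE test, and the DSMB is an advisory expert body, not a count-based trigger.

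Most of this stands, and it limits the size. It does not close the gap. An SAE report can arise from the interventionist route, the only path described for confirmed SAEs leads to the by-arm table, and nothing says whether events known only from that route are counted there. Masked collectors do not protect events that enter through an interventionist advised by an unblinded clinician. The SAE form and Manual of Procedures are not among the documents, so a source field may already exist; if so, the gap is only in the reporting rule.

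A reader might infer that PC will look less safe by construction. The documents do not support that: they never say that off-schedule reports are counted, and the route matters only for events the forms miss.

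**Conclusion.** The concern holds as a possible bias against PC, not a certain one. Opportunity to report is very unequal (about 30 contacts against one), an SAE report can start from such a contact, and the by-arm report has no rule on source. The effect is confined to events missed by five scheduled forms. It is probably small overall, and most plausible for the musculoskeletal class and for participants who miss visits but still take calls.

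The size cannot be derived from the documents. With an assumed 90% capture by the forms the ratio is at most 1.11, and with full capture it is 1.00. Larger figures might be inferred by assuming lower capture (70% capture with 75% recovery gives 1.32), but nothing in the documents anchors 70%. Nor does the 90% follow-up rate show that 10% of SAEs are lost, since a later visit can pick up an event from a missed one. That the DSMB would act against PC on such a difference is likewise not supported.

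**What to change.** - Add a source field to the SAE record: scheduled visit form, off-schedule contact, or both.
- Continue to send every SAE to the DSMB.
- State that the between-arm comparison uses events recorded on the scheduled visit forms common to all arms. An event recorded there counts even if it was first mentioned at an intervention contact; otherwise PC would be under-counted.
- Show events known only through off-schedule contacts in a separate column by arm.
- Leave individual safety follow-up and expedited reporting as they are.

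The cost is one extra field and one extra table column, and the DSMB reads two counts instead of one.
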